### **RESEARCH ETHICS COMMITTEES**

23. The research protocol must be submitted for consideration, comment, guidance and approval to the concerned research ethics committee before the study begins. This committee must be transparent in its functioning, must be independent of the researcher, the Sponsor and any other undue influence and must be duly qualified. It must take into consideration the laws and regulations of the country or countries in which the research is to be performed as well as applicable international norms and standards but these must not be allowed to reduce or eliminate any of the protections for research subjects set forth in this Declaration.

The committee must have the right to monitor ongoing studies. The researcher must provide monitoring information to the committee, especially information about any serious adverse events. No amendment to the protocol may be made without consideration and approval by the committee. After the end of the study, the researchers must submit a final report to the committee containing a summary of the study's findings and conclusions.

#### **PRIVACY AND CONFIDENTIALITY**

24. Every precaution must be taken to protect the privacy of research subjects and the confidentiality of their personal information.

#### **INFORMED CONSENT**

25. Participation by individuals capable of giving informed consent as subjects in medical research must be voluntary. Although it may be appropriate to consult family members or community leaders, no individual capable of giving informed consent may be enrolled in a research study unless he or she freely agrees.

26. In medical research involving human subjects capable of giving informed consent, each potential subject must be adequately informed of the aims, methods, sources of funding, any possible conflicts of interest, institutional affiliations of the researcher, the anticipated benefits and potential risks of the study and the discomfort it may entail, post-study provisions and any other relevant aspects of the study. The potential subject must be informed of the right to refuse to participate in the study or to withdraw consent to participate at any time without reprisal. Special attention should be given to the specific information needs of individual potential subjects as well as to the methods used to deliver the information.

After ensuring that the potential subject has understood the information, the physician or another appropriately qualified individual must then seek the potential subject's freely-given informed consent, preferably in writing. If the consent cannot be expressed in writing, the non-written consent must be formally documented and witnessed.

All medical research subjects should be given the option of being informed about the general outcome and results of the study.

27. When seeking informed consent for participation in a research study the physician must be particularly cautious if the potential subject is in a dependent relationship with the physician or may consent under duress. In such situations the informed consent must

---

be sought by an appropriately qualified individual who is completely independent of this relationship.

28. For a potential research subject who is incapable of giving informed consent, the physician must seek informed consent from the legally authorised representative. These individuals must not be included in a research study that has no likelihood of benefit for them unless it is intended to promote the health of the group represented by the potential subject, the research cannot instead be performed with persons capable of providing informed consent, and the research entails only minimal risk and minimal burden.
29. When a potential research subject who is deemed incapable of giving informed consent is able to give assent to decisions about participation in research, the physician must seek that assent in addition to the consent of the legally authorised representative. The potential subject's dissent should be respected.
30. Research involving subjects who are physically or mentally incapable of giving consent, for example, unconscious patients, may be done only if the physical or mental condition that prevents giving informed consent is a necessary characteristic of the research group. In such circumstances the physician must seek informed consent from the legally authorised representative. If no such representative is available and if the research cannot be delayed, the study may proceed without informed consent provided that the specific reasons for involving subjects with a condition that renders them unable to give informed consent have been stated in the research protocol and the study has been approved by a research ethics committee. Consent to remain in the research must be obtained as soon as possible from the subject or a legally authorised representative.
31. The physician must fully inform the patient which aspects of their care are related to the research. The refusal of a patient to participate in a study or the patient's decision to withdraw from the study must never adversely affect the patient-physician relationship.
32. For medical research using identifiable human material or data, such as research on material or data contained in biobanks or similar repositories, physicians must seek informed consent for its collection, storage and/or reuse. There may be exceptional situations where consent would be impossible or impracticable to obtain for such research. In such situations the research may be done only after consideration and approval of a research ethics committee.

## USE OF PLACEBO

33. The benefits, risks, burdens and effectiveness of a new intervention must be tested against those of the best proven intervention(s), except in the following circumstances:

Where no proven intervention exists, the use of placebo, or no intervention, is acceptable; or

Where for compelling and scientifically sound methodological reasons the use of any intervention less effective than the best proven one, the use of placebo, or no intervention is necessary to determine the efficacy or safety of an intervention and the patients who receive any intervention less effective than the best proven one, placebo,

---

or no intervention will not be subject to additional risks of serious or irreversible harm as a result of not receiving the best proven intervention.

Extreme care must be taken to avoid abuse of this option.

#### **POST-TRIAL PROVISIONS**

34. In advance of a clinical trial, sponsors, researchers and host country governments should make provisions for post-trial access for all participants who still need an intervention identified as beneficial in the trial. This information must also be disclosed to participants during the informed consent process.

#### **RESEARCH REGISTRATION AND PUBLICATION AND DISSEMINATION OF RESULTS**

35. Every research study involving human subjects must be registered in a publicly accessible database before recruitment of the first subject.
36. Researchers, authors, sponsors, editors and publishers all have ethical obligations with regard to the publication and dissemination of the results of research. Researchers have a duty to make publicly available the results of their research on human subjects and are accountable for the completeness and accuracy of their reports. All parties should adhere to accepted guidelines for ethical reporting. Negative and inconclusive as well as positive results must be published or otherwise made publicly available. Sources of funding, institutional affiliations and conflicts of interest must be declared in the publication. Reports of research not in accordance with the principles of this Declaration should not be accepted for publication.

#### **UNPROVEN INTERVENTIONS IN CLINICAL PRACTICE**

37. In the treatment of an individual patient, where proven interventions do not exist or other known interventions have been ineffective, the physician, after seeking expert advice, with informed consent from the patient or a legally authorised representative, may use an unproven intervention if in the physician's judgement it offers hope of saving life, re-establishing health or alleviating suffering. This intervention should subsequently be made the object of research, designed to evaluate its safety and efficacy. In all cases, new information must be recorded and, where appropriate, made publicly available.

## 13.2 Appendix 2

### Slit Lamp Examination

The examination will be performed at every Visit with the slit lamp using a beam of 1.0 mm height and 1.0 mm width with the beam at maximum luminance and using the high powered lens if using Haag-Streit model slit lamp. If alternate model used, center to assure a 1.0 mm by 1.0 mm window with high magnification is achieved.

This procedure will be the same for all patients observed at the investigator's center.

- Anterior Chamber Cells

Grade	Cells in field
0	0
0.5+	1-5
1+	6-15
2+	16-25
3+	26-50
4+	>50

- Anterior Chamber Flare

Grade	Description
0	None
1+	Faint
2+	Moderate (iris and lens details clear)
3+	Marked (iris and lens details hazy)
4+	Intense (fibrin or plastic aqueous)

- Chemosis

Grade	Description
0	None
1	Mild
2	Moderate
3	Severe

- Bulbar conjunctival injection

Grade	Description
0	None
1	Mild
2	Moderate
3	Severe

- Ciliary injection

Grade	Description
0	None
1	Mild
2	Moderate
3	Severe

- Corneal edema

Grade	Description
0	None
1	Mild
2	Moderate
3	Severe

- Keratic precipitates

Grade	Description
0	None
1	Mild

2	Moderate
3	Severe

- Other: Any other sign of ocular inflammation encountered by the investigators (e.g. hypopion, anterior chamber fibrinoid reaction, miosis, papilar or follicular conjunctival reaction, corneal neovascularization). Their severity will not be registered.

### 13.3 Appendix 3

#### Intraocular Pressure

##### Calibration of Tonometer

The Goldmann tonometer shall be used for IOP measurements. The tonometer must be calibrated before first use and calibration will be checked by the investigator prior to measuring IOP for each patient, with the weight system at 0, 2, and 6 grams as supplied by the manufacturer. When the calibration steps provide readings within  $\pm 0.5$  mmHg of the target value for each weight, the tonometer is considered adequately calibrated. The investigator must maintain written documentation (e.g., unit model or serial number, calibration date, name/initial of person performing calibration, indication of pass or fail) of the calibration of each tonometer throughout the study period.

##### IOP Measurement

IOP will be taken as follows:

1. Anaesthetize the selected eye of the patient.
2. Stain with sodium fluorescein.

*NOTE – step may be combined by using an anesthetic to which sodium fluorescein has already been added.*

3. Set the tonometer drum to a force corresponding to an IOP of 10 mmHg. Wherever possible, do not touch the eyelid with the fingers to open the palpebral aperture. If the palpebral aperture is not wide enough to allow the tonometer cone to make contact, instruct the patient to open their eyes wider.
4. Direct the patient to view a distance fixation point.

*NOTE – If distance fixation cannot be maintained and **near fixation is used, this fact should be recorded.***

5. Measure the IOP for the mean of the ocular pulse and remove the tonometer from the eye.
6. Repeat steps if the measurement was not valid due to the following reasons:
  - The patient felt a sensation
  - The eyelid was touched
  - The fluorescein ring was too broad or too small
  - Any other circumstances suggesting that the measurement may have been inaccurate
7. If there is any evidence that the anesthetic is no longer fully effective, then re-administer anesthetic.
8. Record the IOP, as the mean of 3 valid measures. Measure and record means for both eyes.

#### 13.4 Appendix 4

##### Eye Pain - Visual Analogue Scale (VAS)

Please assess the eye pain by ticking the scale, which describes eye pain the best.

---

**13.5 Appendix 5****Discomfort Assessment**

Please assess the severity of the eye discomfort by using the following scale.

Grade	Description
0	None
1	Mild
2	Moderate
3	Severe

---

### 13.6 Appendix 6

#### Photophobia - Visual Analogue Scale (VAS)

Please assess the photophobia by ticking the scale, which describes photophobia the best.

## ABBREVIATIONS

AE	Adverse Event
AESI	Adverse Event of Special Interest
ATC	Anatomical Therapeutic Chemical
BCVA	Best-Corrected Visual Acuity
BMI	Body Mass Index
CSR	Clinical Study Protocol
eCRF	Electronic Case Report Form
FAS	Full Analysis Set
ICH	International Conference on Harmonization
IMP	Investigational Medicinal Product
IOP	Intraocular Pressure
MedDRA	Medical Dictionary for Regulatory Activities
MMRM	Mixed Model of Repeated Measures
NSAID	Non-Steroidal Anti-Inflammatory Drug
PP	Per Protocol
PT	Preferred Term
Q1	25th percentile
Q3	75th percentile
QID	Four times a day (Quater In Die)
REML	Restricted Maximum Likelihood
SAE	Serious Adverse Event
SAF	Safety Analysis Set
SAP	Statistical Analysis Plan
SOC	System Organ Class
STEAE	Serious Treatment-Emergent Adverse Event
SUN	Standardization of Uveitis Nomenclature
TEAE	Treatment-Emergent Adverse Event
VAS	Visual Analog Scale
WHO	World Health Organization

## 1 INTRODUCTION

This Statistical Analysis Plan (SAP) is based on Clinical Study Protocol (CSP) Version 2.0 FINAL Amendment 1 dated [February 26, 2020].

## 2 STUDY OBJECTIVES

### 2.1 Primary Objective

To assess the effect of clobetasol propionate ophthalmic nanoemulsion 0.05% on ocular inflammation associated with cataract surgery after one week of treatment.

### 2.2 Secondary Objectives

Key secondary objective

Efficacy:

- To assess the effect of clobetasol propionate ophthalmic nanoemulsion 0.05% on eye pain associated with cataract surgery after one week of treatment.

Other secondary objectives

Efficacy:

- To assess the effect of clobetasol propionate ophthalmic nanoemulsion 0.05% on ocular inflammation associated with cataract surgery
- To assess the effect of clobetasol propionate ophthalmic nanoemulsion 0.05% on eye pain and on eye discomfort associated with cataract surgery

Safety:

- To evaluate the safety and tolerability of clobetasol propionate ophthalmic nanoemulsion 0.05%

### 3 ENDPOINTS

#### 3.1 Primary Efficacy Endpoint

- Proportion of patients with anterior chamber cell grade of “0” (absence of cells) compared to placebo at Day 8.

Anterior chamber cell grade will be assessed by the investigator during slit-lamp examination and will be graded on an adapted 6-point scale proposed by the Standardization of Uveitis Nomenclature (SUN) working group (Table 1).

Table 1. Grading scheme for anterior chamber cells

Grade	Cells in field*
0	0
0.5+	1-5
1+	6-15
2+	16-25
3+	26-50
4+	>50

[figure not shown]
\*Field size is a 1mm by 1 mm slit beam

#### 3.2 Secondary Efficacy Endpoints

Key secondary efficacy endpoint

- Proportion of patients with VAS pain score of “0” (no eye pain) compared to placebo at Day 8.

Eye pain score will be assessed by the patient before any ocular examination and will be scored by ticking on a continuous scale comprised of a 10 cm horizontal line anchored by two verbal descriptions: “no eye pain” (score of 0) and “worst imaginable eye pain” (score of 10).

- Proportion of patients with anterior chamber cell grade of “0” compared to placebo at Day 3, Day 15 and Day 29.

- Change from Baseline to Day 3, Day 8, Day 15 and Day 29 compared to placebo in the proportion of patients with different anterior chamber cell grades.
- Change from Baseline to Day 3, Day 8, Day 15 and Day 29 compared to placebo in the proportion of patients with different anterior chamber flare grades.
- Proportion of patients with anterior chamber cell grade of “≤0.5+” and flare grade of “0” compared to placebo at Day 3, Day 8, Day 15 and Day 29.
- Proportion of patients with anterior chamber cell grade of “≤1+” compared to placebo at Day 3, Day 8, Day 15 and Day 29.
- Proportion of patients with anterior chamber cell grade of “0” and flare grade of “0” compared to placebo at Day 3, Day 8, Day 15 and Day 29.
- Frequency of different signs of ocular inflammation compared to placebo at Baseline, Day 3, Day 8, Day 15 and Day 29.
- Change from Baseline to Day 3, Day 8, Day 15 and Day 29 compared to placebo in the proportion of patients with different signs of ocular inflammation.
- Change from Baseline to Day 3, Day 8, Day 15 and Day 29 compared to placebo in the severity of signs of ocular inflammation.
- Change from Baseline to Day 3, Day 8, Day 15 and Day 29 compared to placebo in the visual analog scale (VAS) photophobia score.
- Change from Baseline to Day 8, Day 15 and Day 29 compared to placebo in Snellen best-corrected visual acuity (BCVA) score.
- Change from Baseline to Day 3, Day 8, Day 15 and Day 29 compared to placebo in the VAS pain score.
- Proportion of patients with VAS pain of “0” compared to placebo at Day 3, Day 15 and Day 29.
- Change from baseline to Day 3, Day 8, Day 15 and Day 29 compared to placebo in the proportion of patients with different discomfort grades.
- Proportion of patients with no discomfort (“None”) compared to placebo at Day 3, Day 8, Day 15 and Day 29.
- Change over time in the VAS pain score reported in the patients’ diaries compared to placebo.

See previous section 3.1 for anterior chamber cell grade and key secondary efficacy endpoint of this section for eye pain VAS score.

- **Anterior chamber cell flare** will be assessed by the investigator during slit-lamp examination and will be graded on a 5-point scale proposed by SUN working group.

Table 2. The SUN working group grading scheme for anterior chamber flare

Grade	Description
0	None
1+	Faint
2+	Moderate (iris and lens details clear)
3+	Marked (iris and lens details hazy)

4+	Intense (fibrin or plastic aqueous)
----	-------------------------------------

- **Signs of ocular inflammation** (chemosis, bulbar conjunctival injection, ciliary injection, corneal edema, keratic precipitates) will be assessed by the investigator during slit-lamp examination. Additionally, the severity of these signs of ocular inflammation will be assessed.

Table 3. Signs of ocular inflammation. Chemosis, bulbar conjunctival injection, ciliary injection, corneal edema and keratic precipitates.

Grade	Description
0	None
1	Mild
2	Moderate
3	Severe

Other: The severity of any other sign of ocular inflammation encountered by the investigators (e.g. hypopion, anterior chamber fibrinoid reaction, miosis, papilar or follicular conjunctival reaction, corneal neovascularization) will not be analyzed. They will only be shown in the listings.

- Monocular visual acuity will be completed with the patient's best correction vision in place using the standardized visual acuity measurement **Snellen Test**.
- **The eye discomfort** will be assessed by using the following categorical scale (Table 4)

Table 4. Eye discomfort

Grade	Description
0	None
1	Mild
2	Moderate
3	Severe

- The photophobia VAS is a single-item continuous scale comprised of a 10 cm horizontal line anchored by two verbal descriptors, one for each symptom extreme. For photophobia intensity, the scale is anchored by "no photophobia" (score of 0) and "worst imaginable photophobia" (score of 10 cm). The photophobia VAS is completed by the patient:

### 3.3 Secondary Safety Endpoints

- Number, frequency and severity of adverse events (AEs) up to Day 29.
- Number, frequency and severity of serious AEs (SAEs) up to Day 29.
- Proportion of patients discontinuing the study due to AEs.
- Proportion of patients discontinuing the study due to lack of efficacy.
- Change from Baseline to Day 3, Day 8, Day 15 and Day 29 compared to placebo in intraocular pressure (IOP).
- Change from Baseline to Day 3, Day 8, Day 15 and Day 29 compared to placebo in physical and eye examination parameters and vital signs.
- Use of concomitant medications up to Day 29

The IOP will be assessed in both eyes using the Goldmann applanation tonometry method (for details see Appendix 3 of CSP).

[figure not shown]

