## 4. OVERALL DESIGN AND PLAN OF THE STUDY

### 4.1 Overview

This is a phase 3, randomized, parallel-group, double-masked, placebo-controlled, multicenter study.

This study will compare the efficacy and safety of clobetasol propionate ophthalmic nanoemulsion 0.05% to placebo (vehicle), when administering one drop QID during 14 days after routine unilateral cataract surgery.

Approximately a 15% of screening failures is expected. Overall, 210 patients are planned to be randomized into the study. They will be screened across 20 centers in the US. Patients who experience postoperative inflammation on the first day following routine cataract surgery and who meet all other eligibility criteria will be randomized to one of two study groups in a 2:1 ratio to receive either clobetasol propionate ophthalmic nanoemulsion 0.05% (N=140) or placebo (N=70) for the treatment of inflammation and pain associated with cataract surgery.

Patients will undergo routine cataract surgery according to the investigator's normal procedures.

The day of the cataract surgery will be considered Day -1 of the study, whereas the day of the randomization and the first administration of the IMP will be considered Day 1 of the study.

Six study visits are planned: Visit -1 (Screening; Day  $-7 \pm 3$  days), Visit 1 (Baseline; Day 1, 24h after the surgery), Visit 2 (Day 3 + 1 day), Visit 3 (Day 8  $\pm 1$  day), Visit 4 (Day 15  $\pm 2$  days), and Visit 5 (Day 29  $\pm 2$  days) (Table 1). An attempt should be made to schedule patients at approximately the same time during the day at each study visit.

If a patient wants to discontinue from the study, he/she will be treated according to the clinical practice. Patients who discontinue the study treatment will be requested to continue attending their remaining study visits. If the patient does not accept and wants to discontinue from the study, they will be encouraged to at least attend the Early Termination Visit (Section 4.3.2.8) as soon as possible.

An informed consent form (ICF) must be obtained from each patient prior to the commencement of any study procedure. All patients must be given ample time to review the ICF and to ask any question related to the study prior to their participation. All participant patients will be provided with a copy of the signed ICF.

[figure not shown]

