### 5.3 **Withdrawal, Premature Discontinuation of Study Medication, and Replacement of Patients**

Patients are free to discontinue their participation in the study at any time. Additionally, patients may be withdrawn from study at any time, if deemed necessary by the investigator

(after discussion with the Medical Monitor). Withdrawal from the study will not affect or prejudice the patients' further care or treatment.

Potential reasons for withdrawal of patients from this study are:

- The decision of a patient to withdraw informed consent
- Patient is lost to follow-up (Section [5.3.1](#))
- Potential reasons for premature discontinuation of study medication include, but are not limited to: Occurrence of a treatment-emergent AE (TEAE) or considerable worsening of an AE that, in the opinion of the investigator in consultation with the Medical Monitor and Sponsor, represents an unacceptable risk to the patient if he/she continues to receive study medication. The investigator must follow the patient until the AE resolves or satisfactorily stabilizes
- Administration of a rescue medication. Any patient placed on rescue therapy will discontinue the use of the IMP (see Sections [6.7.1](#) and [6.7.2](#))
- Patient's failure to comply with protocol requirements or study related procedures
- In case of pregnancy. The investigator will continue the follow-up of the patient until the end of the pregnancy
- Any surgery (different from the actual routine cataract surgery on the study eye) in the study or contralateral eye

In any case of premature discontinuation of study medication, the investigator must make extensive efforts to ensure that the patient will attend all his/her remaining study visits until study completion (at Visit 5), aiming to collect the most complete efficacy and safety data.

The reason and date the patient is withdrawn from the study will be documented in the eCRF (e.g. lost to follow-up, consent withdrawn, AEs, etc.).

If a patient is withdrawn from the study, the investigator should attempt to complete all discharge procedures (including the Early Termination Visit; Section [4.3.2.8](#)). All AEs should be followed up according to Section [8.3.6](#).

If a patient is withdrawn from the study, or withdraw his/her consent, all data collected until the time of withdrawal will be used in the analyses, unless this is prohibited by local regulations.

Patients who drop out from the study will not be replaced.

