### 6.7.2 Rescue Medication

Any patients not responding adequately to the IMP may be rescued and placed on alternate therapy (Section [6.7](#)) at the investigator's discretion at any time.

The choice of rescue medication is at the investigator's discretion. Any patient placed on rescue therapy will discontinue the use of the IMP and the investigator must make extensive efforts to ensure that the patient will attend all his/her remaining study visits until study completion, aiming to collect the most complete efficacy and safety data.

Additionally, patients will be asked to phone the study center at any time to speak to a member of the medical personnel should they experience any worsening of ocular conditions or other AEs.

Rescued patients will be considered treatment failures, but the need for rescue therapy will not be considered an AE.

---

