#### **7.4 Secondary Safety Endpoints**

The secondary safety endpoints will be:

- Number, frequency and severity of AEs up to Day 29
- Number, frequency and severity of Serious AE (SAE) up to Day 29
- Proportion of patients discontinuing the study due to AEs
- Proportion of patients discontinuing the study due to lack of efficacy
- Change from Baseline to Day 3, Day 8, Day 15 and Day 29 compared to placebo in IOP
- Change from Baseline to Day 3, Day 8, Day 15 and Day 29 compared to placebo in physical and eye examination parameters and vital signs
- Use of concomitant medications up to Day 29

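### Two safety endpoints count patients leaving the study for AEs or lack of efficacy, but the protocol makes these reasons to stop medication, so treatment stops are undercounted, mainly for lack of efficacy

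*SAP*

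**What the plan says.** Protocol 7.4 lists the endpoint "Proportion of patients discontinuing the study due to AEs". Its companion for lack of efficacy is worded the same way, and SAP 3.3 repeats it: "Proportion of patients discontinuing the study due to lack of efficacy". Both count departures from the study.

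Protocol 5.3 separates two events. The reasons it lists for withdrawal from the study are withdrawn consent and loss to follow-up. An unacceptable AE and rescue come under premature discontinuation of study medication. On rescue it says: "Any patient placed on rescue therapy will discontinue the use of the IMP". For every premature stop of medication it adds that "the investigator must make extensive efforts to ensure that the patient will attend all his/her remaining study visits until study completion". Section 6.7.2 repeats this for patients rescued because of an inadequate response.

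Protocol 4.1 shows how strong the retention rule is: "Patients who discontinue the study treatment will be requested to continue attending their remaining study visits". It also provides for refusal: "If the patient does not accept and wants to discontinue from the study, they will be encouraged to at least attend the Early Termination Visit".

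**The concern.** The endpoint wording and the discontinuation rules no longer describe the same event. The summary of changes suggests how this arose: Amendment 1 moved AEs and rescue from the study-withdrawal list to the medication list, and the two endpoints stayed on study discontinuation. The SAP, written from Amendment 1, carried them over.

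Consider a patient who does not respond, is rescued, stops the drops and attends Visit 5, as the protocol intends. That patient has stopped treatment for lack of efficacy but does not count towards the endpoint named for it. The better the sites retain such patients, the larger the undercount.

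The count also bears on reading the efficacy results. SAP section 5 limits the FAS efficacy analysis to visits on study drug without rescue or prohibited medication. SAP 6.3.7 names discontinuation for AEs, lack of efficacy and rescue as intercurrent events. A reader of either needs to know how many patients in each arm stopped treatment, and why.

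**Working it through.** **1. Which planned output would show a treatment stop?**

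| Output | What it counts | Treatment stop for AE | Treatment stop for lack of efficacy |
|---|---|---|---|
| Endpoints in Protocol 7.4 and SAP 3.3 | Patients leaving the study | Only if the patient also leaves | Only if the patient also leaves |
| Protocol 9.1.5; SAP Table 14.1.3 | Reasons for ending the study early | Only if the patient also leaves | Only if the patient also leaves |
| SAP 6.3.10; Table 14.3.1.6 | TEAEs leading to discontinuation, defined in 6.3.10 as drug withdrawn | Yes | No |
| SAP Table 14.3.5.2 | Treatment duration; doses completed or not, with reasons | Dose level | Dose level |
| SAP 6.3.9; Table 14.3.10.3 | Rescue and prohibited drugs, by drug class and generic name | No | Drug use only |

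The AE tables cannot fill the last column. Protocol 6.7.2 says that needing rescue is not an AE, and note 7 to Protocol Table 1 keeps expected post-surgical inflammation and pain out of AE reporting.

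**2. The plan's own dropout figure.** Protocol 9.1.1 and SAP 4.2 use 4%. From 202 evaluable patients, 202 / 0.96 = 210.4, which agrees with the stated 210 to within rounding. In patients, 0.04 × 210 = 8.4, and 210 − 202 = 8. The SAP calls this the dropout rate. If it covers all reasons and holds, the two endpoints together cannot exceed about 4%, however many patients stop treatment. The protocol calls it loss to follow-up; on that reading it sets no limit on withdrawals for AEs or lack of efficacy.

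**3. Size of the undercount.** The documents give no rate of rescue, treatment discontinuation or retention, so these inputs are assumptions. Let *t* be the share of patients stopping treatment for an AE or lack of efficacy, and *s* the share of those who also leave the study. The endpoints together show *t* × *s* and miss *t* × (1 − *s*). Take *t* from 5% (0.05 × 210 = 10.5 patients) to 30% (0.30 × 210 = 63 patients).

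| *s* | Shown at *t* = 5% | Shown at *t* = 30% | Missed at *t* = 5% | Missed at *t* = 30% |
|---|---|---|---|---|
| 0% | 0% | 0% | 5% | 30% |
| 10% | 0.5% | 3.0% | 4.5% | 27% |
| 25% | 1.25% | 7.5% | 3.75% | 22.5% |
| 50% | 2.5% | 15% | 2.5% | 15% |
| 100% | 5% | 30% | 0% | 0% |

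The undercount disappears only if everyone who stops treatment also leaves the study. The formula ignores patients who finish the 14-day course and leave before Day 29. They would enter the study-level endpoint without being treatment stops, which is another reason to report the two separately.

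**4. Sample size.** Neither endpoint enters the calculation. At 0.22 versus 0.07, 2:1 allocation and 202 patients, the power of the chi-square test is 80.2%, as the plan states to rounding.

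**The case against.** The case on the other side has four parts.

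- **Study withdrawal is not closed off.** Retention is requested, and the patient may refuse (Protocol 4.1). Section 5.3 lets the investigator withdraw a patient from the study and still gives AEs as an example of a recorded withdrawal reason. This stands. A reader might infer that the protocol holds these patients in the study and that both proportions must come out near zero. The documents do not support that: zero requires complete retention, and no retention rate is given.
- **The AE information is not lost.** SAP 6.3.10 and Table 14.3.1.6 report treatment stops due to TEAEs. This stands, so for AEs the problem is a misworded endpoint beside a correct table. A reader might infer that the report would hide patients who stopped because of harm; it would not.
- **Lack of efficacy is partly covered.** Rescued patients are failures in the primary and key secondary analyses, Table 14.2.19 is reserved for sensitivity analysis, and rescue has its own column in a summary table. This stands in part. None of these is a by-arm count of patients who stopped treatment for lack of efficacy.
- **The endpoints can be computed as written**, the two documents agree on them, and SAP 6.3.10 makes safety comparisons descriptive only. This is true and limits the consequence. It does not make study withdrawal the right measure of stopping treatment under Protocol 5.3.

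In the current text of 5.3 the lead-in to the medication list runs on from the withdrawal bullets. I read two lists, as the summary of changes sets them out, and make nothing of the layout.

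**Conclusion.** The mismatch is real and concerns reporting. As worded, the two endpoints will undercount patients who stop treatment for an AE or lack of efficacy whenever some of them remain in follow-up, which is what the protocol asks for. The amount cannot be fixed from the documents. Under the assumed ranges it runs from nothing, if all who stop also leave, to the whole 5% to 30%, if none do. If 4% is the all-cause dropout rate, the two endpoints together are capped near 4% of 210, or about 8 patients.

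The consequence falls mainly on lack of efficacy, which has no by-arm patient count at treatment level anywhere in the planned output. The primary and key secondary analyses, sample size and power do not change.

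**What to change.** In Protocol 7.4 (and the matching synopsis lines) and SAP 3.3, define the endpoints as:

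- proportion of patients discontinuing study medication due to AEs;
- proportion of patients discontinuing study medication due to lack of efficacy, including rescue for inadequate response.

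Add one table to SAP 8.1 giving, by arm, the number and percentage of patients who discontinued study medication, by reason. Keep Table 14.1.3 for study withdrawal by reason, and title the two so that they cannot be confused.

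Check that the eCRF records a reason for stopping medication, because Protocol 5.3 asks explicitly only for the reason for study withdrawal. If it does not, the rescue flag (SAP 6.3.9), the action taken on study medication for each AE (Protocol 8.3.3) and the end date of exposure (SAP 6.3.8) should allow the main categories to be derived; write that derivation into the SAP before unmasking.

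The cost is wording and one table. No visit, assessment or clinical rule changes.
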